11.3.4. Safety

The assessment of safety will be based primarily on the following: AEs, ophthalmic examination, BCVA/LLVA scores (ETDRS), vital signs, laboratory safety (biochemistry and haematology), and [REDACTED]

Adverse Events

Adverse events will be collected and recorded throughout the study and verbatim AE terms will be coded (to preferred terms) using terminology from MedDRA.

A TEAE is defined as an AE that is first identified, or is identified to worsen in intensity, on or after the subject receives the study medication during surgery.

The incidence, maximum intensity, and relationship to study medication or procedure of TEAEs will be summarised by system organ class and preferred term, according to dose and route of administration, as appropriate, and classified as systemic or ocular (Treated [Study Eye]/Untreated [Fellow Eye] or Both eyes).

All AEs, SAEs, AESIs, AEs leading to discontinuation, and deaths will be listed.

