### 1.2. Study objectives and endpoints

Study objectives and related endpoints are described in Table 1 below.

[figure not shown]
**Table 1** Objectives and related endpoints

Objectives	Evaluation Criteria
Primary	
To evaluate the safety of GT005 at 3 doses	

Incidence of ocular and non-ocular treatment-emergent AEs (TEAEs) and treatment-emergent serious AEs (TESAEs) over 48 weeks

Secondary	
To evaluate the long-term safety of GT005 at 3 doses	

Incidence of ocular and non-ocular treatment-emergent AEs (TEAEs) and treatment-emergent serious AEs (TESAEs) up to 240 weeks

To evaluate the effect of GT005 on anatomical and functional visual outcomes	

Best corrected visual acuity (BCVA) and low luminance visual acuity (LLVA) score via the early treatment diabetic retinopathy study (ETDRS) chart up to 240 weeks

Macular sensitivity as assessed by Mesopic Micropertimetry up to 240 weeks

Change in GA area size as assessed by fundus autofluorescence (FAF) up to 240 weeks

To evaluate the performance of the Orbit SDS (US only)	

Rate of successful delivery of balanced salt solution (BSS) or BSS PLUS to the subretinal space

Rate of successful delivery of GT005 to the subretinal space

To evaluate the safety of the Orbit SDS (US only)	

Incidence of device-related AEs and SAEs

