### 3.2. Missing data

There will be no imputation of missing data performed except for GA area growth analysis, which will be based on MMRM model and thus missing data will be implicitly imputed assuming Missing at Random (MAR). All data recorded on the CRF will be included in data listings that will accompany the clinical study report.

Missing adverse event (AE) dates are imputed as follows:

- If AE end year is missing, or AE is ongoing, the end date will not be imputed.
- If AE end month is missing, then AE end date = min(31 Dec of AE end year, date of study discontinuation/completion).
- If the AE end day is missing, then AE end date = min(Last day of the AE end month, date of study discontinuation/completion).
- If AE start year is missing and AE end date < TRT date, then AE start date = earliest visit date
- If AE start year is missing and AE end date => TRT date or ongoing, then AE start date = TRT date
- If both AE start and end dates are missing and AE is not ongoing, both dates are set to TRT date.
- If AE start year < TRT year or AE start year > TRT year, and
  - month is missing, then AE start date = 01 Jan of AE start year
  - day is missing, then AE start date = 01 of AE start month-year
- If AE start year = TRT year, and
  - month is missing and AE end date < TRT date, then AE start date = 01 Jan AE start year
  - month is missing and AE end date => TRT date or ongoing, then AE start date = TRT date
  - month < TRT month or month > TRT month, then AE start date = 01 of AE start month-year
  - month = TRT month, then AE start date = min(TRT date, AE end date)

The same algorithm will be applied to impute start and end of concomitant medication.

The imputed dates will only be used to classify events, medications, or procedures as treatment emergent, concomitant or concurrent. Imputed dates will only be used in the table analyses. Listings will display the available date data. Missing dates in medical history will not be imputed except the date of initial diagnosis of GA which will apply the same date imputation algorithm mentioned above.

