### 3.9. Safety Analyses

#### 3.9.1. Adverse events

Analyses of adverse events will be performed in the SAF for treatment-emergent adverse events (TEAE). TEAEs are adverse events that are first identified or worsened after receiving the study treatment. Only treatment-emergent adverse events will be presented in the summary tables. Adverse events will be coded using the MedDRA dictionary and presented by system organ class (SOC) and preferred term (PT). The number (and proportion) of patients with TEAEs will be summarized by treatment dose and administration route at each analysis timepoint according to Table 5. AEs occurred after surgery for treatment administration and before deferred GT005 administration will be listed and included in footnotes of relevant TEAE summary tables.

**Table 5** TEAE summaries by treatment dose per administration route (if applicable)

TEAE summary	AE categories		
	Ocular AE in the study eye	Ocular AE in the fellow eye	Non-ocular AE
All AEs by primary SOC and PT	Y	Y	Y
All AEs by maximum severity	Y	Y	Y
AEs related to study treatment by SOC and PT	Y		Y
AEs related to surgical procedure by SOC and PT	Y		Y
AEs related to Orbit SDS procedure by SOC and PT	Y		Y
SAEs by SOC and PT	Y	Y	Y
SAEs related to study treatment by SOC and PT	Y		Y
SAEs related to surgical procedure by SOC and PT	Y		Y
SAEs related to Orbit SDS procedure by SOC and PT	Y		Y

All adverse events occurring in the study will be listed in subject data listings. By-subject listings will also be provided for the following: subject deaths; serious adverse events;

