### 4. CHANGES TO PLANNED ANALYSES

As of this date, there have been no changes between the protocol-defined statistical analyses and those presented in this statistical plan.

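### The surgery- and Orbit-related adverse-event tables count only treatment-emergent events, so procedure complications before the injection, or at a deferred first attempt, drop out of the counts

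*SAP*

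**What the plan says.** **Which events are tabulated.** SAP Section 3.9.1 defines the events by receipt of GT005: "TEAEs are adverse events that are first identified or worsened after receiving the study treatment". It then limits the tables: "Only treatment-emergent adverse events will be presented in the summary tables". Table 5 is a list of TEAE summaries. Its rows include AEs and SAEs related to the surgical procedure and AEs and SAEs related to the Orbit SDS procedure.

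**Deferred dosing.** The same section says that AEs arising after surgery but before a deferred administration will be listed and put in footnotes to the relevant TEAE tables. All AEs in the study go into subject listings.

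**Endpoints.** The primary endpoint is explicitly treatment-emergent: "Incidence of ocular and non-ocular treatment-emergent AEs (TEAEs) and treatment-emergent serious AEs (TESAEs) over 48 weeks". The secondary endpoint for Orbit safety (SAP Section 1.2; Protocol Section 2) is the incidence of AEs and SAEs related to the device, and no treatment-emergent condition is attached. Protocol Section 9.4 makes events related to the Orbit cannulation procedure device-related.

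**Events during surgery.** The protocol synopsis (Number of Subjects) and Section 7.1 give an AE during surgery as an example of why GT005 administration might be deferred.

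**Protocol TEAE definition.** Protocol Section 11.3.4 uses slightly different words: an AE that is "first identified, or is identified to worsen in intensity, on or after the subject receives the study medication during surgery". SAP Section 4 nevertheless states that "there have been no changes between the protocol-defined statistical analyses and those presented in this statistical plan".

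**The concern.** A treatment-emergent cut-off at the injection suits the question of what GT005 does. It does not suit the question of what the operation or the device does, because exposure to those starts with the procedure. Under the SAP, complications in the part of the operation that precedes the injection cannot enter the tables meant to describe surgical and device safety. The same holds for everything at a first attempt that ended without dosing. A complication serious enough to stop dosing is among the most informative events about the delivery method, and it is one that the tables leave out. Following the SAP as written can therefore understate procedure-related incidence on both routes, and device-related incidence for Orbit.

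**Working it through.** The documents give no AE rate, so there is no plan figure to reproduce. The check sets the definitions side by side and then works out what one subject is worth.

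**1. Where each kind of procedure-related event falls.** Events B to D are assumed not to worsen after the injection; if they did, they would become TEAEs.

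| Event judged related to surgery or Orbit | TEAE, SAP 3.9.1 | TEAE, Protocol 11.3.4 | Counted in Table 5 | Within the device endpoint as worded (Orbit) |
|---|---|---|---|---|
| A. After the injection, same day | Yes | Yes | Yes | Yes |
| B. During surgery, before the injection, dosing goes ahead | No | No | No | Yes |
| C. During a first attempt, dosing deferred | No | No | No | Yes |
| D. After that attempt, before the later dosing | No | No | No (footnote and listing) | Yes |

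The footnote rule describes D. Read literally it does not reach C, because C arises during surgery and not after it. It does not reach B at all. A footnote in any case leaves the numerator unchanged.

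**2. How firm the exclusion is.** The SAP does not say whether AE onset time is used. If only dates are compared and onset on the treatment date counts, B would in practice be counted. C and D would still be excluded whenever the first attempt was on an earlier day than dosing. The deferred case is therefore the firmer part of the finding.

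**3. What one subject is worth.** Maximum cohort sizes are in Protocol Section 3.1.

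- Orbit, Cohorts 5 to 7: 5 + 5 + 20 = 30, so 1/30 = 3.3 percentage points.
- Transvitreal, Cohorts 1 to 4: 3 × 5 + 20 = 35, so 1/35 = 2.9 points.
- Check: 30 + 35 = 65, the planned enrolment.

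This applies to a subject whose only event in the row precedes the injection. Tables are by dose within route, so each denominator will be smaller and the step larger. The dose split in Cohorts 4 and 7 is not fixed, so I give no figure by dose.

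**4. The date rule for TEAEs.** SAP Section 3.2 sends uncertain onsets to the treatment date in four branches, for example "If AE start year is missing and AE end date => TRT date or ongoing, then AE start date = TRT date", and says that imputed dates serve to classify events as treatment-emergent. I applied the rules to 14 partial-date patterns, and 7 landed on the treatment date:

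| Comparison with treatment date | Imputed onsets counted as TEAEs | Complete onset date on the day of surgery |
|---|---|---|
| onset ≥ treatment date | 7 of 7 | counted |
| onset > treatment date | 0 of 7 | not counted |

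The imputation serves its stated purpose only under ≥. SAP Section 3.1.1 points the same way, since it makes the treatment date Day 1 and groups it with later dates. The SAP does not state the operator.

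**The case against.** **Following the protocol.** Protocol Section 11.3.4 itself plans to summarise relationship to the procedure among TEAEs, so Table 5 does not depart from that section. This stands. The mismatch is with the device endpoint as worded, and with the protocol synopsis, which promises reporting of all AEs recorded throughout, including by relationship to the procedure.

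**Nothing is hidden.** All AEs are listed, and cases between surgery and deferred dosing are footnoted. This also stands, and it limits the harm. But the endpoint is an incidence, and listings and footnotes do not enter one.

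**The stronger reading.** A reader might infer from the missing *on or* in the SAP definition that events on the day of surgery fall out of the primary endpoint. The documents do not support that. Both definitions are tied to receipt of GT005 and not to a calendar day; the protocol's words are "on or after the subject receives the study medication during surgery". An event an hour after the injection is a TEAE under either, and the literal difference is the instant of injection. The imputation rules and the Day 1 convention also imply that treatment-date onsets count. Loss would occur only if *after* were programmed as a strict date comparison. What remains is an undeclared difference in wording and an unstated operator.

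**Conclusion.** The point holds for the surgery- and Orbit-related tables. As written, they omit procedure- and device-related events before the injection and at a deferred first attempt, although the device endpoint carries no such limit and the protocol expects that such events can happen. The direction is towards understating incidence.

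The size is not known. It is 3.3 points per affected subject in an Orbit group of 30, and no document says how many subjects would be affected; any assumed share of early events would be a guess. For same-day events the conclusion also assumes that onset can be ordered against the injection. For a deferred first attempt on an earlier day it needs no such assumption.

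The primary endpoint is not shown to lose events. The TEAE wording there needs a clarification, not a change of analysis.

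**What to change.** 1. In SAP Section 3.9.1 and Table 5, for the rows on AEs and SAEs related to the surgical procedure and to the Orbit SDS procedure, count events with onset from the start of the first surgical procedure, including a first attempt after which dosing was deferred. Keep the TEAE rule for the other rows. Label the tables so that the two counting periods are plain.
2. In Section 3.9.1, restore the protocol's on-or-after wording. State that an onset date on or after the treatment date is treatment-emergent unless onset is documented as before the injection, and say whether onset time is used. This agrees with Section 3.2.

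The cost is two or three sentences and one table rule. No new data are needed: the protocol collects AEs from consent with an assessment of relationship to the procedure, and the SAP must already identify deferred cases for its footnote. Reported procedure- and device-related incidence may rise slightly. The change keeps the Safety Analysis Set, so a subject whose surgery began but who never received GT005 stays outside these tables; a note to the tables should say so.

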#### 3.9.2. Visual Acuity (BCVA and LLVA)

Best corrected visual acuity (BCVA), low-luminance visual acuity (LLVA) and low-luminance deficit (LLD) scores via the ETDRS Chart will be summarized as actual and change from baseline values over time (visit) by eye,

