Cataract formation is associated with any vitrectomy procedure. In a published study from [Feng 2014], cataract appeared in approximately 40% of patients following pars plana vitrectomy and resulted in a cataract extraction over the following 2 years. In publicly available safety data, Voretigene Neparvovec, a subretinally delivered AAV2-RPE65 for the treatment of RPE65 retinal dystrophy, was administered in 81 eyes and of those, 11 eyes (14%) from seven subjects had documented progression of existing cataract or formation of new cataract. Three subjects had their cataract successfully extracted and other cataract cases did not receive elective extraction procedures [Voretigene Neparvovec FDA ACM 2017]. The study population of advanced AMD subjects is expected to have a mean age above or equal to 60 years and therefore may have already undergone a cataract extraction. At screening, subjects participating in this GT005 study and assessed as likely to require cataract surgery during the 12-month study period will not be included, or will be offered the option of removing their cataract before being (re)screened in the study. Participants who develop cataracts during the study may undergo cataract surgery if deemed clinically necessary; if surgery is performed, it should be carried out at least 4 weeks before the Week 48 visit.

Intraocular pressure elevation is a risk associated with vitrectomy procedures [Chang 2006] and periocular or topical steroids [Kersey 2006]. In publicly available safety data, Voretigene Neparvovec (Luxturna®), had reports of elevation in IOP in 8 of 81 eyes treated (10%). Patients will have IOPs checked at every visit to ensure adequate monitoring and therapies prescribed as needed based on local standard. At screening, subjects with moderate or advanced glaucoma in the study eye will not be included in the study to minimise this risk.

Worsening of vision is an uncommon risk associated with the surgical procedure or vitreous tap and could be the result of endophthalmitis or retinal damage. [REDACTED]

[REDACTED]

[REDACTED]

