3. STUDY DESIGN

3.1. Overall Study Design and Plan Description

This is an open label FIH Phase I/II multicentre study to evaluate the safety, dose response and efficacy of GT005 in subjects with GA due to AMD. The study will be conducted in four parts; Part 1 (Cohorts 1 to 3): dose-escalation, Part 2 (Cohort 4): dose-expansion, Part 3 (Cohorts 5 to 6): dose-escalation with the Orbit SDS, and Part 4 (Cohort 7): dose-expansion with the Orbit SDS.

Parts 1 and 2 (Cohorts 1 to 4) will deliver GT005 via the standard transvitreal procedure and Parts 3 and 4 (Cohort 5 to 7) will deliver GT005 via the Orbit SDS.

The Orbit SDS is a 510(k) cleared device in the US whereby Parts 3 and 4 (Cohorts 5 to 7) will only be used at US sites.

An overview of the study design is provided in [Figure 1: Overview of the Study]. Approximately 65 subjects will be enrolled: up to five in each of Cohorts 1 to 3, up to 20 in Cohort 4, up to five in each of Cohorts 5 and 6, and up to 20 in Cohort 7.

Part 1 (Cohorts 1 to 3; dose-escalation) will test three dose Cohorts (████████████ vg) of up to five subjects per Cohort. A minimum of three subjects per dose Cohort will be required to evaluate the safety of the respective dose. Sentinel dosing will be applied whereby there will be a minimum of 14 days separation between dosing of the first and second subject of each dose Cohort, to assess any acute reactions to surgery and short-term tolerability to GT005 prior to dosing the remaining subjects in each dose Cohort. Dose escalation will be evaluated by a DSMB and will be assessed based on the Week 5 data for the first three subjects dosed in Cohorts 1 and 2. The DSMB will review the Week 5 safety data for the first three subjects dosed in Cohort 3 prior to dosing in further cohorts. The DSMB can be called upon by the Sponsor to perform safety evaluations as needed.

Subjects will receive a single subretinal injection of GT005 at one of three dose levels:

- Low dose: ██████████
- Mid dose: ██████████
- High dose: ██████████

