4.3. Exclusion Criteria

Subjects must not enter the study if any of the following exclusion criteria are fulfilled:

1. Have evidence or history of CNV in the study eye. Subjects are permitted to have CNV in the fellow eye defined as either:
 - a. Non-exudative/sub-clinical fellow eye CNV identified at screening, or

- b. Known history of fellow eye CNV with either ≥ 2 years since diagnosis or with no active treatment required in 6 months prior to screening
- 2. Presence of moderate/severe non-proliferative, diabetic retinopathy or worse in the study eye
- 3. Have history of vitrectomy, sub-macular surgery, or macular photocoagulation in the study eye
- 4. History of intraocular surgery in the study eye within 12 weeks prior to Screening (Visit 1). [REDACTED]
- 5. Have clinically significant cataract that may require surgery during the study period in the study eye
- 6. Presence of moderate to severe glaucomatous optic neuropathy in the study eye; uncontrolled IOP despite the use of more than two topical agents; a history of glaucoma-filtering or valve surgery is also excluded
- 7. Axial myopia of greater than -8 diopters in the study eye
- 8. Have received any investigational product for the treatment of GA within the past 6 months or 5 half-lives (whichever is longer), other than nutritional supplements such as the age-related eye disease study (AREDS) formula
- 9. Have received a gene or cell therapy at any time
- 10. Have a contraindication to the specified protocol corticosteroid regimen
- 11. Are unwilling to use two forms of contraception (one of which being a barrier method) for 90 days post-dosing, if relevant
- 12. Active malignancy within the past 12 months, except for: Appropriately treated carcinoma in situ of the cervix, non-melanoma skin carcinoma, or prostate cancer with a stable prostate-specific antigen (PSA) ≥ 12 months
- 13. Have any other significant ocular or non-ocular medical or psychiatric condition which, in the opinion of the Investigator, may either put the subject at risk or may influence the results of the study
- 14. Cohorts 5 to 7 only: presence of metallic objects or implanted stimulator devices in or near the head, including cochlear implants, deep brain stimulators, vagus nerve stimulators, and other implanted electrodes or stimulators

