Additionally, there is a known risk of cataract associated with any vitrectomy procedure. A published review from [Feng 2014] shows cataract to be common following pars plana vitrectomy with about 40% of patients requiring a cataract extraction over the following 2 years.

These do not require reporting as AESIs.

Device Specific Adverse Events:

Serious injury means an injury or illness that:

1. Is life-threatening,
2. Results in permanent impairment of a body function or permanent damage to a body structure, or
3. Necessitates medical or surgical intervention to preclude permanent impairment of a body function or permanent damage to a body structure. Permanent means irreversible impairment or damage to a body structure or function, excluding trivial impairment or damage.

For the reporting purposes of this study, a serious injury related to the device is considered an SAE.

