11.1. Sample Size

As this is a FIH exploratory Phase I/II study, no formal sample size has been calculated.

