### 3. STATISTICAL METHODS

#### 3.1. General information

Two interim analyses and a clinical study report (CSR) are planned. First interim analysis will include data up to Week 72 from cohorts 1-4 with GT005 delivered via the transvitreal procedure. Second interim analysis will include data from cohorts 1-4 up to Week 96 and from Orbit SDS administration cohorts 5-7 up to Week 48. Clinical study report will be based on the analysis of all variables specified in this SAP from all 7 cohorts on data over 96 weeks.

All outputs will be incorporated into Word files and PDF files, sorted and labeled according to the International Conference on Harmonisation (ICH) recommendations, and formatted to the appropriate page size(s).

Tabulations will be produced for appropriate demographic, baseline, efficacy, biomarker assay, and safety parameters. For categorical variables, summary tabulations of the number and percentage within each category (with a category for missing data) of the parameter will be presented. For continuous variables, the number of observations, mean, median, quartiles, standard deviation, standard error (SE), minimum and maximum values will be presented. Where appropriate, 95% confidence intervals (CIs) for point estimates of the mean or proportion will be provided. Data will be listed and summarized using descriptive statistics by dose, by route of administration, and by assessment visits as appropriate. Efficacy and biomarker assay data will additionally be summarized by CFI rare variant and broad GA subgroups. All ocular evaluations and ocular adverse events, where appropriate, will be presented by eye (Study Eye, Fellow Eye).

No formal statistical hypothesis testing will be performed for this study.

Medical history, concurrent procedures and adverse events will be coded using the Medical Dictionary for Regulatory Activities (MedDRA). Prior and concomitant medications will be coded using World Health Organization (WHO) Drug Reference List dictionary version Mar 2020.

All statistical analyses will be performed using SAS statistical software (Version 9.4), unless otherwise noted.

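### BCVA, LLVA and low-luminance deficit change is summarised with no account of lens status or cataract surgery, although the protocol names cataract as a known risk of vitrectomy and permits extraction on study.

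*SAP*

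**What the plan says.** BCVA and LLVA up to 240 weeks are secondary criteria for the effect of GT005 on visual outcomes (Protocol Section 2; SAP Table 1), so they are more than safety variables. Their visible analysis is SAP 3.9.2: BCVA, LLVA and low-luminance deficit "scores via the ETDRS Chart will be summarized as actual and change from baseline values over time (visit) by eye", by dose and by route, with plots of mean change and 95% confidence intervals. The synopsis names the untreated fellow eye as the comparator, and Protocol 11.3.4.1 and 11.3.4.2 together call for treated-minus-untreated differences in acuity.

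On cataract, Protocol 9.1 cites "about 40% of patients requiring a cataract extraction over the following 2 years" after pars plana vitrectomy. Section 1.6.1.2.1 cites the same review. It adds that 11 of 81 eyes (14%) given another subretinal AAV2 product had new or progressed cataract, with extraction in three subjects, and notes that subjects here may already have had a cataract removed.

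The visible text offers two protections. Exclusion criterion 5 reads "Have clinically significant cataract that may require surgery during the study period in the study eye". For cataract that develops on study, Section 1.6.1.2.1 allows surgery and says "if surgery is performed, it should be carried out at least 4 weeks before the Week 48 visit".

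The SAP's long list of ocular baseline characteristics (3.5) has no lens status. SAP 2.2 has a data rule for one intervention that could disturb efficacy values, alternative GA treatment in the study eye, and none for cataract surgery.

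**The concern.** A phakic eye that has a vitrectomy can lose letters as a cataract grows and regain them when it is removed. Neither change is an effect of GT005 on the retina. SAP 3.9.2 averages both into change from baseline at each visit.

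The fellow eye does not have the study surgery, so the contrast with it absorbs any excess of lens change in the study eye. Protocol 1.6.2 expects no gain in acuity from GT005. A rise after extraction could therefore be misread, and a true loss could be masked.

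The Week 48 rule keeps the immediate surgical period away from one visit. It does not deal with letters lost before extraction, or with letters regained by an extraction done before Week 44 (48 − 4). No visible rule covers Weeks 72 and 96, which fall within the 96 weeks of data planned for the clinical study report (SAP 3.1), or the later visits. Week 96 is also close to the 2-year horizon of the cited review.

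**Working it through.** **The plan's own figures.** 11/81 = 0.136, which rounds to the stated 14%. The 40% is cited without counts and cannot be recomputed. The transvitreal maximum follows from "up to five in each of Cohorts 1 to 3, up to 20 in Cohort 4": 3 × 5 + 20 = 35. The Orbit maximum is 2 × 5 + 20 = 30, and 35 + 30 = 65, as stated. There is no power calculation to reproduce: "no formal sample size has been calculated".

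**Inputs not in the documents.** The phakic share *f* of study eyes is taken as 25% to 100%, and the net letter change *d* per affected eye as 5 to 15.

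**Formulas**, with *p* the cited rate:
- expected affected transvitreal study eyes = 35 × *f* × *p*
- shift in the transvitreal mean = *f* × *p* × *d*
- chance of at least one affected eye among five = 1 − (1 − *f* × *p*)^5

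| *p* | *f* | Affected of 35 | Mean shift at *d* = 5 / 10 / 15 letters | At least 1 of 5 |
|---|---|---|---|---|
| 40% | 100% | 14.0 | 2.0 / 4.0 / 6.0 | 0.92 |
| 40% | 50% | 7.0 | 1.0 / 2.0 / 3.0 | 0.67 |
| 40% | 25% | 3.5 | 0.5 / 1.0 / 1.5 | 0.41 |
| 13.6% | 100% | 4.8 | 0.7 / 1.4 / 2.0 | 0.52 |
| 13.6% | 50% | 2.4 | 0.3 / 0.7 / 1.0 | 0.30 |
| 13.6% | 25% | 1.2 | 0.2 / 0.3 / 0.5 | 0.16 |

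The two rates count different events: the 40% is extraction, the 13.6% is new or worse cataract. The shift is a magnitude only. Cataract lowers acuity and extraction raises it, so the sign depends on the mix at each visit. An eye that develops a cataract and has it removed may end near its baseline.

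**Small cells.** In a dose-by-route cell of five, one eye changing by 10 letters moves the mean by 10/5 = 2 letters, whatever the cataract rate.

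**Scale against sampling error.** With an assumed SD of 10 letters, the 95% half-width for a mean of 35 is 3.4 letters (2.7 at SD 8, 5.2 at SD 15). A 2-letter shift lies inside that, but the interval does not allow for it.

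**Can a reader recover lens status from other outputs?** Cataract events appear in the SAP Table 5 adverse-event tables by eye, dose and route, but are not linked to acuity by visit. Medical history and concomitant procedures are listed without a summary table (SAP 3.6, 3.11). The protocol lists cataract grading among the ocular safety variables to be summarised, again apart from acuity. One subsection of SAP 3.9 is redacted and might show lens data.

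**The case against.** The strongest reply is that an all-values summary is legitimate. Cataract caused by the procedure is a consequence of receiving GT005 that way, and "No formal statistical hypothesis testing will be performed for this study". Results are already split by eye, dose and route, no formal cohort comparison is planned, and a careful reader of the listings could trace an odd rise in acuity to lens surgery. This stands for the safety reading, so the existing table should stay. It does not answer the functional-effect objective, which uses the same numbers to describe what GT005 does to vision. The harm is to interpretation and not to an error rate.

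Four stronger readings are tempting, and the documents do not support them.
- A reader might infer that the protocol expects 40% extraction in this trial. It cites that figure as a known risk, beside the 14%, and notes possible prior extraction.
- A reader might infer that the Week 48 rule is the only protection. Exclusion criterion 5 also keeps out study eyes with significant cataract that may need surgery. It cannot prevent cataract that develops after vitrectomy.
- A reader might infer that the distortion falls on the treated eye alone. Criterion 5 applies only to the study eye, so a fellow eye may enter with cataract and have it removed.
- A reader might infer that the two routes differ. The protocol ties the risk to vitrectomy, and the visible Orbit text (1.6.1.3) names only inflammation and transient vision loss as shared risks. But that section is partly redacted and no Orbit cataract rate is visible.

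**Conclusion.** The gap is real: the SAP handles neither baseline lens status nor on-study cataract surgery in the acuity summaries that serve a secondary functional objective. Two protections reduce the effect without removing it.

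At 50% phakic and 10 letters net per affected eye, the transvitreal mean moves by about 2.0 letters at the 40% rate and 0.7 at 13.6%. Over the whole assumed range it moves by 0.2 to 6.0 letters. Phakic share and letters per eye are assumptions, and the direction is open. Any difference in cataract between routes would confound a comparison of the route summaries, but such a difference is an inference. This is a change that should be made because it is cheap and aids interpretation; the planned tables remain valid as descriptions of what was observed.

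A separate wording conflict needs attention. Section 1.6.1.2.1 says a subject "assessed as likely to require cataract surgery during the 12-month study period will not be included", while exclusion criterion 5 refers to the study period without a length, in a study that follows subjects for 5 years. This is an eligibility matter and does not bear on the size above.

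**What to change.** - **SAP 3.5:** add baseline lens status (phakic or pseudophakic) for the study eye and the fellow eye, by dose and route.
- **SAP 3.9.2:** keep the all-values summary. Add a supplementary summary of BCVA, LLVA and low-luminance deficit change by route and eye, (a) in eyes pseudophakic at baseline and (b) in all eyes with values after cataract extraction in that eye set aside. Report the number of extractions by route, eye and visit.
- **Protocol:** reconcile the look-ahead period in Section 1.6.1.2.1 with exclusion criterion 5.

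Give (a) more weight, because it rests on a baseline characteristic. Summary (b) conditions on a post-baseline event and still carries letters lost before extraction. Do not cut at the first worsening of lens grade: the AREDS system has three opacity scales, and the plan does not say which would count.

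The cost is programming for the added tables. AREDS lens grade in both eyes, ocular surgical history and concomitant procedures are already collected. The downside is small numbers, so show the restricted summaries by route and not by dose cell.
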